3.1. Inclusion Criteria

- 1) A confirmed prior diagnosis of AML and underwent an alloHSCT as a form of consolidation in a morphologic complete remission
- 2) ECOG performance status 0-2
- 3) Ability to give informed consent
- 4) In agreement to use an effective barrier method of birth control to avoid pregnancy during the study and for a minimum of 30 days after study treatment, for all male and female patients who are fertile
- 5) Age ≥ 18 years
- 6) Prior treatment with a CD123-targeted therapy will be allowed assuming the patient did not have a grade 3 or 4 adverse reaction to prior use of this treatment
- 7) Normal thyroid function (defined by either a TSH within the reference range, a TSH above the reference range with a free T4 within the reference range, or a TSH below the reference range with both a free T4 and total T3 within the reference range) or normal thyroid tests on supplementation or treatment (defined as a TSH within the reference range)
- 8) Patients should be at least 30 days from transplant with morphologic evidence of disease progression on bone marrow biopsy
- 9) A population of blasts with expression of CD123 is noted.
- 10) Peripheral blast count $\leq 20,000/\text{mm}^3$ at time of initiation on Cycle 1 Day 1

3.2. Exclusion Criteria

- 1) No evidence of donor engraftment (100% patient DNA in bone marrow or peripheral blood after alloHSCT based on either an unsorted specimen or CD3 sorted).
- 2) Active AML in CNS or testes
- 3) Patients with active, uncontrolled infection. If an infection is controlled and under treatment, then the patient may become eligible.
- 4) Patients with active acute or chronic GVHD requiring GVHD therapy (mycophenolate mofetil, tacrolimus, sirolimus, or steroids) within 30 days
- 5) Patients without active acute or chronic GVHD requiring prophylactic GVHD therapy (mycophenolate mofetil, tacrolimus, sirolimus, or steroids) within 30 days
- 6) Inadequate end organ function defined as:

- Hepatic-AST, ALT, and alkaline phosphatase > 3.5X ULN, bilirubin >2.5X ULN
- Renal-creatinine clearance <60 mL/min using the modified Cockcroft-Gault formula
- Cardiac-Recent myocardial infarction within 6 months, Congestive Heart Failure with EF <50%, active pericarditis or myocarditis
- Pulmonary-Need for supplemental oxygen to maintain oxygen saturation >92%
- Adrenal-Adrenal insufficiency requiring physiologically-dosed steroids

7) Women who are pregnant or lactating

8) Previous or known hypersensitivity to biological agents or constituents of flotetuzumab or its source material

9) Concurrent use of any other investigational drugs

10) Uncontrolled infection with human immunodeficiency virus (HIV) or chronic infection with hepatitis B virus or hepatitis C virus (HCV)

11) Any active untreated autoimmune disorders (with the exception of vitiligo, resolved childhood atopic dermatitis, prior Grave's disease now euthyroid clinically with stable supplementation)

12) Previous treatment with radiotherapy or an immunotherapeutic agent in the 14 days prior to study drug administration (Cycle 1 Day 1) or 5 half-lives, whichever is longer

13) Requirement, at the time of study entry, for concurrent steroids > 10 mg/day of oral prednisone or equivalent, except steroid inhaler, nasal spray, or ophthalmic solution

14) Use of granulocyte colony stimulating or granulocyte-macrophage colony stimulating factor in the 2 weeks prior to study drug administration

15) Prior adverse event with CD123 therapy necessitating therapy discontinuation

3.3. Inclusion of Women and Minorities

The proposed study is open to both men and women and to all racial/ethnic subgroups. There is no explicit mention of different treatment effects in male and female patients or in different racial/ethnic subgroups in the literature. Therefore, this study will not have separate accrual targets for these groups.

3.4. Informed Consent

All patients eligible for the study must be evaluated by one of the study investigators. Informed consent must be obtained and the consent form signed. An eligibility checklist will be completed following fulfillment of the on-study requirements for laboratory work and eligibility criteria. For enrollment of non-English-speaking candidates, the policies and procedures mandated by the JHM IRB will be followed as listed on the following website:

<https://irb.jhmi.edu/Guidelines/nonenglishconsent.html>

4. Study Design and Schedule

4.1. Pre-Treatment Plan

A complete history and physical examination and list of medications will be documented for each patient within two weeks of enrollment. A bone marrow aspirate or biopsy confirming a diagnosis of relapsed AML will be documented in the electronic medical record. A bone marrow aspirate/biopsy documenting a CR (<5% blasts) must be performed prior to transplantation.

Evaluations within 14 days of beginning therapy will include:

1. A history including a list of active medications and physical exam including body height and weight
2. Hematologic studies: complete blood count with differential cell counts.
3. Chemistry panel (including electrolytes, creatinine, uric acid, albumin, total protein, calcium and phosphate)
4. Thyroid Stimulating Hormone
5. Lactate Dehydrogenase
6. Hepatic panel: serum AST, ALT, alkaline phosphatase, total bilirubin, PT/PTT
7. Urinalysis
8. An ECG
9. Pregnancy test (where appropriate)
10. ECOG performance status
11. A bone marrow biopsy and/or aspirate including chimerism testing

4.2. Treatment Schedule

All patients will undergo a bone marrow biopsy prior to enrollment to assess for relapse and must have gross morphologic evidence of relapsed leukemia ($\geq 5\%$ blasts) for enrollment in this group. Patients may enroll at any time after day +30 post-transplant. Patients enrolled on DL1 will receive flotetuzumab by continuous infusion using multi-step lead-in dosing as outlined in

Table 1, and then 500 ng/kg/day on days 7-28. After one cycle, all patients will undergo a bone marrow biopsy to assess response including assessment of MRD. Patients who fail to achieve a CR, CRI, CRh, or MLFS may continue with subsequent induction cycles as a continuous infusion up to a total of five cycles. If there is evidence of response (CR, CRI, CRh, or MLFS) and the toxicities of treatment are acceptable, patients will be eligible for two consolidation cycles as outlined in Table 1. Additional bone marrow biopsies for response assessment will be performed after the second cycle. Results will be censored should patients undergo a second alloHSCT. If there is a need to de-escalate dosing based on toxicity, then patients will be enrolled on DL-1 using multi-step lead-in dosing as outlined in Table 1, and then 300 ng/kg/day on days 5-28 of the first cycle and days 1-28 of subsequent cycles.

Table 1			Dosing Schedule	
Cycle	Week	Days	ng/kg/day	
Induction: Cycle 1				
1	1	Day 1	DL1	DL-1
		Day 2	30	30
		Day 3	60	60
		Day 4	100	100
		Day 5	200	200
		Day 6	300	300
		Day 7	400	300
	2	Days 8-14	500	300
	3	Days 15-21	500	300
	4	Days 22-28	500	300
Consolidation/Reinduction: Cycle 2 and beyond				
2	1	Days 1 – 28	500	300

4.3 Flotetuzumab Dosing

Flotetuzumab dosing in this trial will be based on maximum tolerated dose schedule as determined in the phase I trial and subsequently modified with multi-step lead-in dosing during the first week of treatment.^{60,61} During week 1 of treatment, patients will receive flotetuzumab via continuous infusion using multi-step lead-in dosing as described in table 1. If they tolerate this lead-in dose, then they will be escalated to a dose of 500 ng/kg/day on days 7-28 for DL1 or

300 ng/kg/day on days 5-28 for DL-1. Dosing in subsequent cycles will be as outlined above without multi-step lead-in dosing.

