4.4 Timing of Initiation and Criteria for Subsequent Treatment

After HSCT the majority of acute GVHD occurs in the first 60 days. To ensure patients are stable prior to initiating flotetuzumab therapy, the study will start no sooner than day 30 post-transplant and must be off of immunosuppression for minimum of 30 days prior to initiating treatment. Approximately half of relapses occur within the first year after SCT, with 80% occurring within the first two years.⁶³

Patients eligible for subsequent cycles of therapy as consolidation or continued induction, must meet the following criteria:

- Peripheral blast count $\leq 20,000/\text{mm}^3$
- Meeting criteria for end organ function as defined in exclusion criteria #6
- Have had resolution to \leq Grade 1 of any non-hematologic adverse event deemed to be possibly, probably, or definitely related to flotetuzumab

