4.7.4. Other Clinically Relevant Adverse Events

If a grade 3 non-hematological adverse event occurs that is deemed by the investigator to be possibly, probably or definitely related to the study drug, then flotetuzumab will be withheld until the toxicity resolves to no more than grade 1 (mild) after which flotetuzumab may be restarted at the previously tolerated dose. If the toxicity persists for more than 14 days, then flotetuzumab will be permanently discontinued. If a grade 4 non-hematological adverse event occurs that is deemed by the investigator to be possibly, probably or definitely related to the study drug, then flotetuzumab should be permanently discontinued.

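### The Cycle 2 dose is fixed whatever dose was reached in Cycle 1, which conflicts with the conditional escalation in 4.3 and the restart rule in 4.7.4

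*Combined protocol and SAP*

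**What the plan says.** **Cycle 1.** Section 4.3 makes the assigned dose conditional: "If they tolerate this lead-in dose, then they will be escalated to a dose of 500 ng/kg/day", or to 300 ng/kg/day at DL-1. It does not define tolerating the lead-in, and it does not say what a patient receives otherwise.

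**After a related Grade 3 non-hematologic event.** Section 4.7.4 withholds the drug until the event is Grade 1 or lower, after which "flotetuzumab may be restarted at the previously tolerated dose". It gives no rule for going back up and none for the next cycle.

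**Later cycles.** The last sentence of 4.3 reads "Dosing in subsequent cycles will be as outlined above without multi-step lead-in dosing". The Table 1 block headed "Consolidation/Reinduction: Cycle 2 and beyond" has a single row, Days 1 to 28, at 500 (DL1) or 300 (DL-1). The text of 4.2 agrees for DL-1: "300 ng/kg/day on days 5-28 of the first cycle and days 1-28 of subsequent cycles". No exception is stated.

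**Starting another cycle.** Section 4.4 says "Patients eligible for subsequent cycles of therapy as consolidation or continued induction, must meet the following criteria". The criteria are blast count, organ function and resolution to Grade 1 or lower "of any non-hematologic adverse event deemed to be possibly, probably, or definitely related to flotetuzumab". The dose reached or tolerated is not among them.

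**The concern.** The Cycle 1 rules let a patient's dose follow what that patient has tolerated. The later-cycle rule does not. The two diverge only for patients who had difficulty in Cycle 1, and for them the plan gives no single answer on Cycle 2 Day 1.

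Two things are at stake. The first is safety. Read literally, the fixed row can take a patient, without lead-in, to a dose above the last one tolerated, although 4.7.1 itself reports that lead-in dosing lowered the risk of cytokine release syndrome (CRS). The second is interpretation. If different clinicians resolve the conflict differently, patients at the same dose level receive different Cycle 2 regimens. Section 8.2 does not make clear whether what follows counts in the DLT tally.

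**Working it through.** The plan offers no figure to reproduce here. The check is a comparison of the rules, followed by simple dose ratios.

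**1. Can a patient finish Cycle 1 below the assigned dose and still start Cycle 2?**

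- *Through 4.7.4.* A related Grade 3 event during the lead-in leads to a hold and then a restart at an earlier step. Nothing directs a later increase. The restart requires the event to have come down to Grade 1 or lower, which is the same threshold as the toxicity item in 4.4. Unless the event recurs or another one appears, a restarted patient has already met that item, so 4.4 does not separate these patients from the rest.
- *Through Table 6.* Each survivable severity tier directs a return to the original rate, but only as tolerated. A patient whose return is not completed by Day 28 also ends below the assigned dose.
- *What may intervene.* Section 4.11 ends treatment for unacceptable adverse events, for inability to tolerate the drug, or on the physician's judgement. Section 4.2 requires acceptable toxicity before consolidation and only permits, rather than requires, further induction. None of these refers to the dose reached.

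The path is therefore open, for a limited group.

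**2. What dose applies on Cycle 2 Day 1?** Table 1 and the last sentence of 4.3 give 500 or 300. Section 4.7.4, if its restart dose is taken to persist, gives something lower. The documents do not say which governs.

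**3. How large is the step if the fixed row is followed?** The extracted Table 1 is offset by one row. Moved up one row, it agrees with the text (500 from Day 7 for DL1, 300 from Day 5 for DL-1), so the offset is not treated as an error. The DL1 sequence is then 30, 60, 100, 200, 300, 400, 500 ng/kg/day.

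Step ratio = next dose / current dose:

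- 60/30 = 2.0
- 100/60 = 1.67
- 200/100 = 2.0
- 300/200 = 1.5
- 400/300 = 1.33
- 500/400 = 1.25

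The largest is 2.0.

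Cycle 2 ratio = fixed Cycle 2 dose / last Cycle 1 dose:

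| Last Cycle 1 dose (ng/kg/day) | DL1 (500) | DL-1 (300) |
|---|---|---|
| 400 | 1.25 | not applicable |
| 300 | 1.67 | 1.0 (assigned dose) |
| 200 | 2.5 | 1.5 |
| 100 | 5.0 | 3.0 |

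The step exceeds the largest lead-in step for a DL1 patient left at 200 or below and for a DL-1 patient left at 100 or below. It does not for a DL1 patient left at 300 or 400, or a DL-1 patient left at 200.

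**4. Does a Cycle 2 event enter the MTD decision?** Assuming 28-day cycles run back to back, Cycle 2 is days 29 to 56 and Cycle 3 is days 57 to 84, both inside the 90 days named in 8.2. The same sentence of 8.2 also speaks of monitoring the first cycle for DLTs. Either reading is possible.

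**The case against.** The case for leaving this alone has several parts.

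- *Dropping the lead-in after Cycle 1 is a deliberate choice.* Table 2 gives a separate Cycle 2 Day 1 premedication schedule, and 6.2.2 says infusion reactions typically occur in the first 48 hours of the first infusion. This stands. For a patient who has been receiving the assigned dose, the omission is not a defect.
- *General brakes exist.* Sections 4.11 and 4.2 may remove some of these patients, so one cannot infer that every patient goes to the assigned dose in Cycle 2. This stands too. But the brakes decide whether treatment continues, not at what dose.
- *CRS is already handled.* A reader might take a Grade 3 CRS that resolves within 72 hours as the typical route. The documents do not support that, because Table 6 directs such a patient back to the original rate. Only an incomplete return leaves a gap.
- *Little is left to affect the MTD.* Most events that trigger 4.7.4 are already DLTs under 6.2.1, and a patient counted once cannot be counted again. An added count needs a restart after an excepted event, such as Grade 3 fatigue or fever. This narrows the statistical consequence; the conflicting dose instruction remains.
- *A Cycle 2 toxicity belongs to DL1.* A reader might say that such an event is not what DL1 tests. Table 1 defines DL1 as including the fixed dose in Cycle 2 and beyond, so it is an outcome of DL1 as written.

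**Conclusion.** The point holds as a conflict between instructions, of moderate severity. It applies to a patient who ended Cycle 1 below the assigned dose, mainly through a 4.7.4 restart, satisfies 4.4 and meets no stopping rule in 4.11. For that patient 4.7.4 and the conditional wording of 4.3 point one way, and Table 1 and the last sentence of 4.3 point the other.

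Its size in dose terms is a 2.5- or 5-fold step for a DL1 patient restarted at 200 or 100 ng/kg/day, against a largest lead-in step of 2-fold. This assumes that the patient stays at the restart dose to the end of Cycle 1 and that the fixed row is then followed.

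Its size for the MTD cannot be stated. One could assume DLT risks with and without the step and compute the chance that a dose level clears with 0 or 1 DLT in 6. The documents give neither risk nor the frequency of the path, so the result would only restate the assumptions. Whether Cycle 2 events count at all depends on which reading of 8.2 is meant.

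**What to change.** 1. Reconcile 4.2 with Table 1, 4.3, 4.4, 4.7.4 and 4.11 so that one instruction applies in Cycle 2 to a patient who did not reach, or was restarted below, the assigned dose. The rule is for the investigators to choose; none is proposed here.
2. In 8.2, state whether events in Cycle 2 that fall within the 90 days count as DLTs.
3. On the DLT form, flag any DLT that follows a Cycle 2 start above the highest dose tolerated in Cycle 1, so that it can be identified when the dose level is judged.

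The cost is a short amendment and one field on a form. No extra patients or procedures are needed.

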4.4 Timing of Initiation and Criteria for Subsequent Treatment

After HSCT the majority of acute GVHD occurs in the first 60 days. To ensure patients are stable prior to initiating flotetuzumab therapy, the study will start no sooner than day 30 post-transplant and must be off of immunosuppression for minimum of 30 days prior to initiating treatment. Approximately half of relapses occur within the first year after SCT, with 80% occurring within the first two years.⁶³

Patients eligible for subsequent cycles of therapy as consolidation or continued induction, must meet the following criteria:

- Peripheral blast count $\leq 20,000/\text{mm}^3$
- Meeting criteria for end organ function as defined in exclusion criteria #6
- Have had resolution to \leq Grade 1 of any non-hematologic adverse event deemed to be possibly, probably, or definitely related to flotetuzumab

4.5. Premedications and Prophylaxis

Based on the clinical experience to date; similar findings from other bispecific molecules, such as blinatumomab; and reported clinical experience with CAR-T therapies, all patients treated with flotetuzumab will receive premedication to prevent or mitigate potential infusion-related reactions. Specific pre-treatment regimens are described below.

Prior to the first dose (Week 1):

All patients are to be treated as described in table 2. No steroids should be administered for infusion-related reaction prophylaxis except as indicated. Patients should receive adequate hydration during study therapy, and the addition of IV fluids to maintain intravascular volume (e.g., 50-100 mL/hr of normal saline) is recommended for at least 48 hours after the start of therapy.

Prior to Week 2 dosing:

The premedication schedule should be followed as described below in table 2. In addition, these premedications should be considered in patients if they are resuming flotetuzumab treatment after a dose interruption lasting > 1 day in Cycle 1.

Steroids should not be administered for infusion-related reaction prophylaxis except as indicated below, but may be used for the treatment of emerging symptoms as clinically appropriate. Patients should receive adequate hydration during study therapy, and the addition of IV fluids to maintain intravascular volume (e.g., 50-100 mL/hr of normal saline) is recommended for at least 48 hours after the start of therapy in Week 2.

Prior to subsequent doses (after Week 2):

The premedication schedule should be followed as described below in table 2.

For infusion-related reactions during the course of treatment, supportive care measures should be implemented as outlined in [Section 4.7.1](#).

IV fluids should be administered for inpatients in all schedules unless contraindicated and adequate oral hydration should be emphasized for patients treated as outpatients.

Table 2 **Premedications/Prophylaxis for CRS/IRR**

Medication	7-day Continuous Infusion Schedule (Induction: Cycle 1*)			
	Week 1	Week 2	Week 3	Week 4
Acetaminophen (1000 mg PO) Or Paracetamol (1000 mg PO) Or Ibuprofen (400 mg PO)	Day 1: 30 minutes prior to dosing; Then q 8 hrs for 48 hours Day 7: 30 minutes prior to syringe change; Then q 8 hrs for 48 hrs	None	None	None

Diphenhydramine (25-50 mg IV or PO) or equivalent	Day 1: 30 minutes prior to dosing; Then q 8 hrs for 48 hrs Day 7: 30 minutes prior to syringe change; Then q 8 hrs for 48 hours	None	None	None
Famotidine (20 mg IV) or equivalent	Day 1: 30 minutes prior to dosing; Then q 12 hrs for 48 hrs Day 7: 30 minutes prior to syringe change; Then q 12 hrs for 48 hours	None	None	None
Dexamethasone (or equivalent)	Day 1: 10-20 mg IV up to 30 minutes prior to dosing; Then 4 mg IV at 12 hours after dosing Day 7: 10 mg IV up to 30 minutes prior to syringe change; Then 4 mg 12 hours later	None	None	None
7-day Continuous Infusion Schedule (Reinduction/Consolidation: Cycle 2 and Beyond)*				
Acetaminophen (1000 mg PO) Or Paracetamol (1000 mg PO) Or Ibuprofen	Day 1: 30 minutes prior to dosing; Then q 8 hrs for 48 hours	None	None	None

Diphenhydramine (25-50 mg IV or PO) or equivalent	Day 1: 30 minutes prior to dosing; Then q 8 hrs for 48 hrs	None	None	None
Famotidine (20 mg IV) or equivalent	Day 1: 30 minutes prior to dosing; Then q 12 hrs for 48 hrs	None	None	None
Dexamethasone (or equivalent)	Day 1: 10-20 mg IV up to 30 minutes prior to dosing; Then 4 mg IV at 12 hours after dosing	None	None	None

* If dosing is interrupted for >24 hours during continuous infusion, the premedication schedule for Week 1 of the Reinduction/Consolidation: Cycle 2 and Beyond schedule should be followed.

4.6. Study Parameters

The studies planned during patient evaluation and therapy are listed in Table 3. This represents the basic follow-up plan and will change based on patient condition. All attempts will be made to collect all correlative studies, however, due to laboratory constraints (weekends, holidays, laboratory emergencies or staffing difficulties) and patient constraints (related to intercurrent disease, transportation, or inadequate sample), some samples will not be collected or will not be suitable for evaluation. A patient will be considered suitable for evaluation independent of the availability of correlative study material. A variation of +/- 3 days for all study testing and visits is permitted.

Table 3: Study Calendar

Pre-Treatment		Cycle 1			Subsequent Cycles			End of Treatment	Post-Treatment Follow-up
Parameter	Pre-treatment	Day 1	Day 8, Day 15, Day 22	Day 28	Day 1	Day 8, Day 15, Day 22	Day 28		
Screening/Administrative									
Informed Consent	X								
Pre-Treatment		Cycle 1			Subsequent Cycles			End of Treatment	Post-Treatment Follow-up
Parameter	Pre-treatment	Day 1	Day 8, Day 15, Day 22	Day 28	Day 1	Day 8, Day 15, Day 22	Day 28		
Demography/Medical History	X								
Eligibility Criteria	X								
Study Drug Administration									
Flotetuzumab		X	X		X	X			
Safety Assessments									
Physical Examination	X	X			X			X	
ECOG Performance Status	X	X			X				
Vital Signs	X	X			X				
Weight ¹	X	X			X				
Height	X								
ECG	X								
Concomitant Medications	Continuous from the time of signing of ICF until at least 30 days after the last dose of flotetuzumab								
Adverse Events	Continuous from the time of signing of ICF until at least 30 days after the last dose of flotetuzumab								
Laboratory Assessments									
CBC with Differential	X	X	X	X	X	X	X	X	
PT, PTT	X	X			X				

CMP	X	X	X	X	X	X	X	X	
Magnesium	X	X			X				
Phosphate	X	X			X				
LDH	X								
HBV surface antigen and hepatitis C (antibodies)	X								
HIV Antibody	X								
Serum HCG or urine pregnancy test for applicable women only	X	X			X				
Pre-Treatment		Cycle 1			Subsequent Cycles			End of Treatment	Post-Treatment Follow-up
Parameter	Pre-treatment Within 14 days prior to Day 1	Day 1	Day 8, Day 15, Day 22	Day 28	Day 1	Day 8, Day 15, Day 22	Day 28		
Peripheral Blood and Bone Marrow studies for MRD	X			X			X		
Bone Marrow studies for chimerism	X			X			X		
Peripheral Blood and Bone Marrow studies for immunologic correlates	X		X (Day 15 ONLY/P B ONLY)	X			X (Cycle 2 ONLY)		X (at 6 and 12 months post-transplant and relapse) ⁴
Peripheral Blood serum samples for Cytokine Measurement	X ⁵	X ⁵	X ⁵						
Disease Evaluations									
Bone Marrow aspirate/biopsy	X			X			X	X	

MRD Assessment via Peripheral Blood and Bone Marrow ²	X			X			X	X	
Survival, subsequent therapy, other malignancies ³									X
¹ Must be assessed prior to dosing on Day 1 of each specified cycle, in case of weight loss of >10% within a cycle, the dose of study drug must be recalculated.									
² See section 5.5. MRD assessment will be performed on bone marrow using MFC as previously described by Gerber et al., where any detectable disease will be considered positive. ^{35,54} Samples will be sent for standard-of-care MFC from the bone marrow aspirate, and if a bone marrow aspirate cannot be obtained, then samples will be sent from the peripheral blood for standard-of-care MFC.									
³ This data will be obtained through standard-of-care provider visits that occur following alloHSCT.									
⁴ The correlative samples will be collected at the time of the patient's standard of care bone marrow biopsies that are performed at 6 and 12 months after transplant. There is considerable variability in the time at which these are performed.									
⁵ Samples will be collected pre-dose and once per infusion bag change.									

